4.0 ELIGIBILITY ASSESSMENT AND ENROLLMENT

4.1 Inclusion Criteria

1. Men and women with histologically confirmed disease as defined by the following:
 - CLL: clonal B-lymphocytosis $\geq 5,000$ cells/ μ L .
 - SLL: lymphadenopathy with the tissue morphology of CLL but that are not leukemic, $< 5,000$ cells/ μ L.
 - Immunophenotypic profile or immunohistochemistry read by an expert pathologist as consistent with CLL. This will include CD5, CD19, and CD20 expression by the CLL cells typically also with CD23 expression, but CD23 negative cases may be included if there is an absence of t (11;14)
2. Active disease as defined by at least one of the following (IWCLL consensus criteria):
 - Weight loss $\geq 10\%$ within the previous 6 months
 - Extreme fatigue
 - Fevers of greater than 100.5°F for ≥ 2 weeks without evidence of infection
 - Night sweats for more than one month without evidence of infection
 - Evidence of progressive marrow failure as manifested by the development of, or worsening of, anemia and/or thrombocytopenia
 - Massive or progressive splenomegaly
 - Massive nodes or clusters or progressive lymphadenopathy
 - Progressive lymphocytosis with an increase of $>50\%$ over a 2-month period, or an anticipated doubling time of less than 6 months
3. Treatment naïve CLL/SLL patients
 - Treatment-naïve CLL indicates no prior anti-CLL therapy. Anti-CLL therapy includes chemotherapies, monoclonal antibodies, and targeted agents with known or reasonably expected anti-leukemic activity.
4. Eastern Cooperative Oncology Group (ECOG) performance status of ≤ 2
5. ANC $> 750/uL$, platelets $> 50,000/uL$
6. Agreement to use acceptable methods of contraception during the study and for 90 days after the last dose of study drug if sexually active and able to bear or beget children
 - Female subjects who are of non-reproductive potential (i.e., post-menopausal by history - no menses for ≥ 1 year; OR history of hysterectomy; OR history of bilateral tubal ligation; OR history of bilateral oophorectomy). Female subjects of childbearing potential must have a negative serum pregnancy test upon study entry.
 - Male and female subjects who agree to use both a highly effective method of birth control (e.g., implants, injectables, combined oral contraceptives, some intrauterine devices, complete abstinence, or sterilized partner) and a barrier method (e.g. condoms, vaginal ring, sponge, etc.) during the period of therapy and for 90 days after the last dose of study drug

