4.2 Exclusion Criteria

- Transformed CLL, including Hodgkin and non-Hodgkin lymphoma
- Active autoimmune hemolytic anemia or thrombocytopenia

- Known bleeding disorders
- Impaired hepatic function: Total bilirubin ≥ 1.5 x upper limit of normal unless due to Gilbert's disease, AST/ALT ≥ 2.5 x institutional upper limit of normal unless due to infiltration of liver, Child-Pugh class B or C
- Impaired renal function: estimated GFR < 30 ml/min/1.73m² based on CKD-EPI
- Life-threatening illness, medical condition or organ system dysfunction which, in the investigator's opinion, could compromise the subject's safety, interfere with the absorption or metabolism of ibrutinib and fludarabine, or put the study outcomes at undue risk
- Concomitant immunomodulatory therapy, chemotherapy, radiotherapy or experimental therapy
- Active Hepatitis B or Hepatitis C infection
- HIV infection
- Female patients who are currently in pregnancy, or unwilling to use acceptable methods of contraception or refrain from pregnancy if of childbearing potential or currently breastfeeding. Male patients who are unwilling to follow the contraception requirements described in this protocol.
- Psychiatric illness/social situations that would limit the patient's ability to tolerate and/or comply with study requirements.
- Unable to understand the investigational nature of the study or give informed consent.
- Individuals < 18 years old
- Known hypersensitivity to any component of ibrutinib or fludarabine
- Requires concomitant anticoagulation with Coumadin (warfarin) or other vitamin K antagonists.
- Prior malignancy, except for adequately treated basal cell or squamous cell skin cancer, in situ cervical cancer, or other cancer from which the subject has been disease-free for ≥ 2 years or which will not limit survival to < 2 years.
- Malabsorption syndrome, disease significantly affecting gastrointestinal function, or resection of the stomach or small bowel or ulcerative colitis, symptomatic inflammatory bowel disease, or partial or complete bowel obstruction.
- History of stroke or intracranial hemorrhage within 6 months before the first dose of study drug
- Major surgery within 4 weeks of first dose of study drug.

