5.8 Special instructions for patients

5.8.1 Immunizations: Live vaccines are contraindicated in this patient population. Subjects who would like to receive other routine non-attenuated vaccinations will be allowed to do so. Patients will be advised not to receive live viral vaccines. The ability to generate an immune response to any vaccine following administration of ibrutinib has not been studied.

5.8.2 Birth control: Subjects with reproductive potential who are sexually active must use acceptable methods of contraception during the study and for 90 days after the last dose of ibrutinib. Examples of acceptable methods of contraception include condoms, implants, injectables, combined oral contraceptives, intrauterine devices, true sexual abstinence, or sterilized partner. Note that that periodic abstinence, e.g., calendar, ovulation, symptothermal, post-ovulation methods or withdrawal, are not acceptable methods of contraception.

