11.2.3 Risks related to CT Scan: CT (computed tomography), sometimes called CAT scan, uses special x-ray equipment to obtain image data from different angles around the body and then uses computer processing of the information to show a cross-section of body tissues and organs. Oral and/or intravenous contrast agents will be used and are usually well tolerated. However, some subjects will experience allergic reactions to intravenous contrast. To lower the risk of allergic reactions, low allergenic contrast agents are administered at NIH clinical center. In addition, subjects will be advised that approximately 2-7% of patients who receive contrast agents will experience a temporary reduction in kidney function lasting up to 2 weeks following infusion and that in rare instances, permanent renal damage can result from the use of the IV contrasting agent. Therefore, in subjects with impaired kidney function, we will not use intravenous contrast.

The amount of radiation subjects will receive from the research scans in this study is 1.3 rem of radiation annually, which is below the guideline of 5 rem (or 0.5 rem in children) per year allowed for research subjects by the NIH Radiation Safety Committee. All female subjects will receive pregnancy testing prior to radiation exposure.

11.2.4 Related to pregnancy and nursing mothers: There are no clinical studies in pregnant women, and it is unknown whether ibrutinib or its metabolites are excreted in human milk. Men and women of child-bearing potential must use highly effective contraceptive (eg, condoms, implants, injectables, combined oral contraceptives, some intrauterine devices [IUDs], sexual abstinence, or sterilized partner) protection while on study and for 90 days after the last dose of study drug. If a female subject or the partner of a male subject becomes pregnant, the sponsor must be notified. Male subjects should refrain from sperm donation.

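### Section 4.1 requires a highly effective contraceptive plus a barrier; section 11.2.4 counts condoms as highly effective with no added barrier, and section 5.8.2 omits the second method

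*Combined protocol and SAP*

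**What the plan says.** Three sections of the protocol set the contraception rule.

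- **Section 4.1, item 6 (inclusion).** The lead-in applies the item to a subject "if sexually active and able to bear or beget children". The bullet on methods accepts "Male and female subjects who agree to use both a highly effective method of birth control". The second half of that requirement, with its duration, reads "and a barrier method (e.g. condoms, vaginal ring, sponge, etc.) during the period of therapy and for 90 days after the last dose". Condoms are not among its examples of highly effective methods; they appear only in the barrier list.
- **Section 11.2.4 (pregnancy and nursing mothers).** Fertile subjects of either sex "must use highly effective contraceptive (eg, condoms, implants, injectables, combined oral contraceptives, some intrauterine devices [IUDs], sexual abstinence, or sterilized partner". The duration is given as "protection while on study and for 90 days after the last dose of study drug". No barrier method is added.
- **Section 5.8.2 (birth control, under the special instructions for patients).** The scope is "Subjects with reproductive potential who are sexually active must use acceptable methods of contraception during the study". The obligation ends 90 days past the final ibrutinib dose. The list of methods is "Examples of acceptable methods of contraception include condoms, implants, injectables, combined oral contraceptives, intrauterine devices, true sexual abstinence, or sterilized partner". A second method is not mentioned.

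Two other sections attach consequences to the rule. Section 4.2 excludes "Male patients who are unwilling to follow the contraception requirements described in this protocol". Section 5.5.3 makes unwillingness to use an acceptable method a reason to stop study drug permanently.

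**The concern.** Sections 4.1 and 11.2.4 are both written as requirements and cover the same kind of subject, yet they classify condoms differently and ask for different numbers of methods. Section 5.8.2 is the text most directly aimed at what patients are told on study, and it leaves out the stricter part of the rule.

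The rule exists to prevent fetal exposure to the study drugs, in female subjects and in partners of male subjects. Section 11.2.4 itself notes that there are no clinical studies in pregnant women, and section 10.1.2 requires partner pregnancies to be reported until 90 days after the last dose. Staff who counsel from 11.2.4 or 5.8.2 could accept less protection than 4.1 demands. The same subject could also be judged compliant or non-compliant according to the section consulted.

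**Working it through.** The plan gives no figure on this point to reproduce. The check is a comparison of texts, followed by simple arithmetic for reach and duration.

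**Texts side by side**

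| | 4.1 item 6 | 11.2.4 | 5.8.2 |
|---|---|---|---|
| Who | Sexually active and fertile | Men and women of child-bearing potential | Sexually active with reproductive potential |
| Methods required | Two: highly effective and barrier | Highly effective; no barrier added | Acceptable methods; second method not stated |
| Where condoms are listed | Barrier only | Highly effective, named first | Acceptable |
| Period | Lead-in: study plus 90 days; two-method bullet: therapy plus 90 days | On study plus 90 days | Study plus 90 days |

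**Test case: a sexually active, fertile subject who uses condoms and nothing else**

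1. Under 4.1 the barrier half is met. The highly effective half is not, because condoms are not offered there and one method cannot fill both places. The subject fails.
2. Under 11.2.4 condoms are a named example of what must be used. The subject passes.
3. Under 5.8.2 condoms are a named example of an acceptable method. The subject passes on a plain reading, although the section does not say that one method is enough.

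**Reverse case.** A sexually active subject who uses a highly effective method from the 4.1 list plus a barrier meets all three sections as regards method. The gap therefore runs one way, toward less protection under 11.2.4 and 5.8.2.

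**Period.** The wording is not identical: the two-method bullet refers to therapy, the other texts to the study. All of them cover therapy plus 90 days, so the conflict exists over at least that span.

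**Reach (section 9.3).** Maximum enrolled = 27 evaluable + up to 5 additional = 32. Section 11.1.1 predicts 66% men: 0.66 × 32 = 21.1, or about 21. That is an expected count of men enrolled, not of condom users. The documents give no share of condom-only users, so none is computed.

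**Duration for an affected subject.** Cycle length is 28 days (section 3.0); the 5-day cycle tolerance in section 5.2 is ignored.

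- Six cycles: 6 × 28 + 90 = 168 + 90 = 258 days.
- Through cycle 27, as listed in section 5.2: 27 × 28 + 90 = 756 + 90 = 846 days; 846 / 365.25 = 2.3 years.
- Longer if ibrutinib continues until progression, as section 3.0 provides.

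These lengths describe the period over which the sections disagree. They do not measure harm.

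**The case against.** The best answer is that 4.1 is an inclusion criterion, so every enrolled subject must satisfy it. Section 11.2.4 sits among the risk descriptions and does not set eligibility, and when one rule is stricter than another the stricter one governs. On that view the defect is one misplaced word in 11.2.4 and an omitted restatement. This has force for entry. It does not settle conduct on study: item 6 records an agreement made at entry, the protocol states no order of precedence, 11.2.4 is phrased as an obligation, and section 4.2 points to the protocol's contraception requirements in general and not to 4.1.

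A second objection is that 5.8.2 is silent, not contradictory. It uses the plural for methods and offers its list as examples. That is right, and the firm contradiction is between 4.1 and 11.2.4. The omission in 5.8.2 still matters because that section instructs patients.

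Third, the risk is reduced by other features. Section 11.1.2 considers pre-menopausal women highly unlikely to present, the predicted median age is 60, and section 6.2 schedules repeated pregnancy tests for women of childbearing potential. These points stand, but they do little for partners of male subjects, and men are expected to be about two thirds of enrollment.

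Fourth, restating the 4.1 bullet literally would require a barrier of an abstinent subject, because abstinence is among its highly effective methods. The restriction in the lead-in to sexually active subjects answers this, provided it is carried over with the rule.

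**Conclusion.** The inconsistency is real and is in the current text. Sections 4.1 and 11.2.4 give incompatible requirements for a condom-only subject, and 5.8.2 fails to state the stricter one. It should be corrected, because the rule protects against fetal exposure and bears on eligibility and on stopping study drug.

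The size is small: no more than 32 subjects, an unknown number of whom would rely on condoms alone, for 258 days or more each if they complete six cycles. The primary endpoints, sample size, error rates and stopping rules are unaffected.

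The conclusion rests on the protocol text alone. The consent pages were not available for this review, so whether they tell subjects about both methods cannot be checked.

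**What to change.** If two methods are intended, which is what 4.1 says:

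- In 11.2.4, remove condoms from the highly effective examples and add the barrier requirement.
- In 5.8.2, state that a highly effective method and a barrier are both needed.
- In both places, keep the 4.1 restriction to sexually active subjects and use one description of the period.

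If the sponsor intends one method to suffice, amend 4.1 item 6 to say so and use the same text in 4.1, 5.8.2 and 11.2.4. The consent form should be checked against whichever rule is chosen.

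The cost is wording in one amendment. No visits, procedures or patients are added.

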4.2 Exclusion Criteria

- Transformed CLL, including Hodgkin and non-Hodgkin lymphoma
- Active autoimmune hemolytic anemia or thrombocytopenia

- Known bleeding disorders
- Impaired hepatic function: Total bilirubin ≥ 1.5 x upper limit of normal unless due to Gilbert's disease, AST/ALT ≥ 2.5 x institutional upper limit of normal unless due to infiltration of liver, Child-Pugh class B or C
- Impaired renal function: estimated GFR < 30 ml/min/1.73m² based on CKD-EPI
- Life-threatening illness, medical condition or organ system dysfunction which, in the investigator's opinion, could compromise the subject's safety, interfere with the absorption or metabolism of ibrutinib and fludarabine, or put the study outcomes at undue risk
- Concomitant immunomodulatory therapy, chemotherapy, radiotherapy or experimental therapy
- Active Hepatitis B or Hepatitis C infection
- HIV infection
- Female patients who are currently in pregnancy, or unwilling to use acceptable methods of contraception or refrain from pregnancy if of childbearing potential or currently breastfeeding. Male patients who are unwilling to follow the contraception requirements described in this protocol.
- Psychiatric illness/social situations that would limit the patient's ability to tolerate and/or comply with study requirements.
- Unable to understand the investigational nature of the study or give informed consent.
- Individuals < 18 years old
- Known hypersensitivity to any component of ibrutinib or fludarabine
- Requires concomitant anticoagulation with Coumadin (warfarin) or other vitamin K antagonists.
- Prior malignancy, except for adequately treated basal cell or squamous cell skin cancer, in situ cervical cancer, or other cancer from which the subject has been disease-free for ≥ 2 years or which will not limit survival to < 2 years.
- Malabsorption syndrome, disease significantly affecting gastrointestinal function, or resection of the stomach or small bowel or ulcerative colitis, symptomatic inflammatory bowel disease, or partial or complete bowel obstruction.
- History of stroke or intracranial hemorrhage within 6 months before the first dose of study drug
- Major surgery within 4 weeks of first dose of study drug.
- Currently active, clinically significant cardiovascular disease such as uncontrolled or symptomatic arrhythmias, Class 3 or 4 congestive heart failure as defined by New York Heart Association Functional Classification, or a history of myocardial infarction, or unstable angina, or acute coronary syndrome within 6 months of screening.
- Subjects who received a strong cytochrome P450 (CYP) 3A inhibitor within 7 days prior to the first dose of ibrutinib or subjects who require continuous treatment with a strong CYP3A inhibitor.

5.0 TREATMENT PLAN

5.1 Drug administration

Ibrutinib is an orally administered product. Study drug ibrutinib administration will take place in the outpatient facility of the NIH clinical center or at the patient's home. The drug dose is 420 mg PO daily. There is one specific dietary restriction to avoid grapefruit juice and Seville oranges due to CYP450 3A4 inhibition. Each dose of ibrutinib is to be taken with 8 ounces (approximately 240mL) of water. The capsule should be swallowed intact and subjects should not attempt to open the capsule or dissolve them in water. Ibrutinib will be given daily until disease progression or intolerable side effects.

Fludarabine is given as an intravenous infusion on cycle 3 and 4. Fludarabine administration will take place in the Clinical Center Day hospital. At the PI's discretion, select subjects may be admitted to the inpatient unit for the first few days of fludarabine infusion. Subjects will have a peripheral line placed. Per PI discretion, a central line may be placed in select patients. Fludarabine dose is 25 mg/m²/day on days 1-5 of cycles 3 and 4. Dosing will be based on actual weight for all patients. No dose adjustment is required based on age. In the event of renal impairment, dose reduction will be as follows;

- Creatinine clearance of 30-70 mL/min/1.73m² using the CKD-EPI equation with actual body weight: Fludarabine will be dose reduced by 20%.
- Creatinine clearance of ≤ 30 mL/min/1.73m² using the CKD-EPI equation with actual body weight: Fludarabine will be held at the discretion of the PI.

5.2 Therapy schedule: All cycles will be 28 (+/- 5) days long.

- Cycle 1 and 2: ibrutinib 420mg PO daily on day 1-28
- Cycle 3 and 4: ibrutinib 420mg PO daily on day 1-28, fludarabine 25mg/m²/day on day 1-5
- Cycle 5 and subsequent cycles up to C27: ibrutinib 420mg PO daily on day 1-28

5.3 Prophylactic Medications:

- Allopurinol 300mg PO once daily (or alternative agent in case the subject cannot tolerate allopurinol) during cycle 3 and 4 on days 1-7 for all subjects
- Sulfamethoxazole/trimethoprim DS PO once daily 3 times per week (or alternative agent in case of sulfa allergy) from cycle 1 to 9 and beyond at the discretion of the PI
- Acyclovir 800 mg PO twice daily or valacyclovir 500mg PO once daily at the discretion of the PI (not mandatory)

5.4 Holding and dose adjustments of study drug administration in the case of treatment related toxicity

5.4.1 Cytopenia:

Drug	Cycle	Condition at the start of cycle	Action*
Ibrutinib	1 and onwards	ANC <500/μL OR PLT <50,000/μL	Check CBC with differential weekly. Hold ibrutinib if cytopenia persists for ≥ 7 days OR if PLT <50,000/μL with bleeding. Resume ibrutinib when ANC ≥750/μL AND PLT ≥50,000/μL. 
 • First occurrence: Resume ibrutinib at 420 mg once daily (original dose). • Second occurrence: Resume ibrutinib at 280 mg once daily. If cytopenia does not recur after 2 cycles of ibrutinib 280 mg once daily, investigator may increase ibrutinib to 420 mg once daily.
Fludarabine	3 and 4	HGB <11 g/dL with indications of autoimmune hemolysis	Omit fludarabine.
		ANC 750 - <1,000/μL OR PLT 50,000 - <75,000/μL	Defer fludarabine and check CBC with differential weekly. Resume fludarabine at original dose when ANC ≥1,000/μL AND PLT ≥75,000/μL. If count recovery does not occur in 8 weeks, omit fludarabine.
		ANC <500/μL, OR PLT <50,000/μL	Defer fludarabine, and check CBC with differential weekly. Resume fludarabine at 20% reduced dose when ANC ≥1,000/μL AND PLT ≥75,000/μL. If count recovery does not occur in 8 weeks, omit fludarabine.

ANC - absolute neutrophil count; PLT – platelet

* Dose delay or reduction is not required if cytopenia is considered related to CLL.

5.4.2 Atrial fibrillation:

- For new-onset atrial fibrillation, ibrutinib will be held until cardiac evaluation has been completed. The decision to restart ibrutinib will be made after the PI and consulting physician determine the subject is sufficiently stable following diagnostic testing and institution of treatment if required.
- Anticoagulation with atrial fibrillation: If anticoagulation is deemed necessary by consulting physician and/or PI, patients will be allowed to start treatment with anti-platelet or anti-coagulant therapies except warfarin. Co-administration with warfarin has been associated with grade 3 or higher bleeding events such as (subdural hematoma, gastrointestinal bleeding, hematuria, and post procedural hemorrhage). Other forms of anti-platelet, anti-coagulant, direct thrombin inhibitors, or factor Xa inhibitors may be used concomitantly with ibrutinib, however the risk of increased bruising or bleeding is unknown. Patients will be counseled and monitored closely for signs of bleeding and/or bruising and will be instructed to contact the research team and primary care physician in the case of any complications.

5.4.3 Non-hematologic toxicities:

- After a grade 3 or higher non-hematological toxicity (despite optimal supportive care) resolves, ibrutinib will be restarted as follows;

Occurrence	Action
1 st	Hold ibrutinib until recovery to Grade \leq 1 or baseline; restart at the original dose level (420mg daily).
2 nd	Hold ibrutinib until recovery to Grade \leq 1 or baseline; restart at one dose level lower (280mg daily).
3 rd	Hold ibrutinib until recovery to Grade \leq 1 or baseline; restart at one dose level lower (140mg daily).
4 th	Discontinue ibrutinib.

- A high number of circulating malignant cells ($>400,000/\mu\text{L}$) may confer increased risk; these subjects should be closely monitored. Administer supportive care such as hydration and/or leukapheresis as indicated. Ibrutinib may be temporarily held, and PI should be contacted.
- In the event that ibrutinib is withheld for a toxicity of 28 consecutive days the study drug should be discontinued. However, if clinical benefit outweighs the risk of restarting treatment then patient may restart study drug after > 28 consecutive days off study drug per PI discretion.
- For fludarabine, after a grade 3 non-hematological toxicity (despite optimal supportive care), when the toxicity resolves to grade 2 or lower and clinical benefit outweighs the risk, treatment can be restarted with 20% dose reduction on the subsequent cycle. Patients experiencing \leq Grade 2 side effects may continue treatment. Supportive measures as appropriate should be taken to minimize side effects. An interruption of study drug administration is permissible. In select cases where a subject has uncomfortable grade 2 toxicities, dose may be reduced by one dose level per PI discretion.

Dose changes must be recorded in the Dose Administration eCRF.

5.4.4 Dose modification for hepatic impaired subjects:

- Ibrutinib is metabolized in the liver and therefore subjects with clinically significant hepatic impairment at the time of screening (Child- Pugh class B or C) are excluded from study participation.
- For subjects with existing chronic mild hepatic impairment (Child-Pugh class A) at enrollment, the starting dose has to be adjusted to a level of 280 mg daily (two capsules).
- For subjects who develop mild liver impairment while on study (Child-Pugh class A), the recommended dose reduction for ibrutinib is to a level of 280 mg daily (two capsules).

- For subjects who develop moderate liver impairment while on study (Child-Pugh class B), the recommended dose reduction is to a level of 140 mg daily (one capsule).
- Subjects who develop severe hepatic impairment (Child-Pugh class C) must hold study drug until resolved to moderate impairment (Child-Pugh class B) or better.
- Subjects who develop acute hepatic toxicity with liver enzymes Grade 3 or higher while on study should be managed per standard dose modification guidelines in Section 5.4.3.

